A geographically dispersed and diverse set of infusion centres in the United Kingdom (UK), Germany, France, Italy, and Spain will be recruited to participate in the study. At each participating centre, de-identified data will be retrospectively abstracted from medical records on non-oncology treatment indication and patient and disease characteristics for all patients receiving MabThera. In addition, a self-administered patient questionnaire will be employed to collect information on patient knowledge about the risk of infections including PML, patient receipt and review of the PAC, and any actions the patient has taken as a result of receiving the PAC.

Description of Study:

Data from medical records will be retrospectively abstracted over a 12-month look back period in the participating infusion centres. Patients will be recruited in the same infusion centres to participate in the patient survey during a 10-month data collection period.

Start Date of Study:

The study start date will be the date of the first data collection: the date on which information on the first study patient from the survey is recorded in the study database or, the date on which retrospective data extraction starts.

End of Study:

The end of the study will be the date on which the last information of the last patient is recorded in the study database.

Population

Patients must meet the following inclusion criteria for study entry:

- Patient is in the centre to receive an infusion for MabThera for a non-oncology indication during the study period
- · Patient is aged 18 years or older
- Patient provides informed consent for medical record abstraction and/or survey participation
- Patient participating in the survey can read and understand English, Spanish, Italian, French, or German, according to the country

No Exclusion criteria will apply for medical record abstraction participation although patients who meet any of the following criteria will be excluded from the survey participation:

- · Patient has previously already completed the MabThera survey
- Patient has participated in the past 12 months in a clinical trial in which MabThera was one of the treatments being evaluated

Variables

Medical record data:

- · Patient demographics
- · Indication for which MabThera has been prescribed
- Disease severity
- · Treatment history

Patient questionnaire data:

- · Patient demographics
- · Patient awareness of potential risk factors
- · Receipt and reading of the PAC

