The index date (start date of medical record abstraction for the first patient) for the study will be selected for each country and correspond to the date when a site becomes aware of the study objectives. After all approvals from national EC and regulatory authorities have been granted, all medical record data will be retrospectively reviewed until the index date; this approach will ensure the data collected are fully reflective of real world administration of MabThera and not influenced by study awareness. The retrospective review of medical records will occur within a 12-month "look-back" period prior the selected index date (i.e., the eligibility period). The observation period for consenting patients corresponds to the interval between the first and last infusion dates of MabThera, if treatment is discontinued before the index date. If the patient is still on MabThera at the index date, then the observation period is the interval between the first infusion date and index date. Furthermore, if a patient stops and re-starts MabThera during the observation period, all repeated treatment intervals will be captured.

Patient Alert Card survey

The PAC survey will be conducted after the index data and concomitantly with the medical record abstraction process. The PAC survey will be completed once by each patient after informed consent has been provided.

Duration of the study

The planned duration of the study (i.e., both medical record and survey data collection) is approximately 16 months after the recruitment of the first patient. This period takes into account 10 months of data collection and a 6 month period between last patient recruited and final study report.

will closely monitor inclusion rates. If projected recruitment rates indicate that patient targets may not be achieved in the planned recruitment period, consideration will be given to extending the recruitment period, initiating additional sites within the 5 existing countries, and/or expanding the study into additional EU countries.

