8.2 POPULATION

Infusion centres that are representative of the non-oncology use of MabThera in the UK, Germany, France, Italy, and Spain will be recruited to participate in the study. Each centre will be expected to retrospectively abstract data from medical records for non-oncology MabThera patients and to enrol an appropriate number of patients who will complete the patient questionnaire component of the study; the target is a total of 100 survey participants per country. The survey participants will be recruited during a 10-month period concomitantly with the medical record abstraction process.

Infusion Centre Eligibility

To participate in the study (DUS and PAC survey), each infusion centre must meet all of the following criteria:

- 1. Administer MabThera to a least 20 patients who would meet the eligibility criteria in the past 12 months; and
- 2. Be able to provide a semi-private space for patient recruitment, the consent process, and completion of the patient questionnaire; and
- Have a staff member available to coordinate study activities.

Patient Eligibility for the study

Patients must meet the following inclusion criteria for study entry:

- 1. Patient is in the centre to receive an infusion for MabThera for a non-oncology indication during the study period
- 2. Patient is aged 18 years or older
- Patient provides informed consent for medical record abstraction and/or survey participation
- 4. Patient participating in the survey can read and understand English, Spanish, Italian, French, or German, according to the country.

No Exclusion criteria will apply for medical record abstraction participation although patients who meet any of the following criteria will be excluded from the survey participation:

- 1. Patient has previously already completed the MabThera survey
- 2. Patient has participated in the past 12 months in a clinical trial in which MabThera was one of the treatments being evaluated.

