8.6 DATA ANALYSIS

Analysis of MabThera off-label use and evaluation of PAC knowledge and utilisation will be descriptive in nature and will entail the tabular display of summary statistics and the frequency distribution of item responses.

A detailed analysis plan describing methods of analysis and presentation, as well as table shells, will be developed prior to starting analysis of data. In addition to describing the analysis of off-label use, for the questionnaire data, the analysis plan will describe any planned comparisons of participants and non-participants. The analysis plan will also describe the following:

- Analysis of subgroups
- · Methods for handling missing data
- Level of statistical precision

All analyses will be performed using SAS 9.2 (or higher) statistical software (SAS Institute Inc., Cary, North Carolina, USA). Programs, logs, and output will be reviewed for accuracy according to relevant standard operating procedures.

The analysis of off-label use will be descriptive and will present MabThera utilisation by indication (RA, SLE/LN, other). Results will be evaluated by site characteristics, including country and geographic region within country, to ascertain any patterns of prescribing by specific indication. The main analysis will be to estimate (with 95% CIs)

^a With an average cluster size of 8 patients, correlation coefficients of 0.15 and 0.30 correspond with design effects of 2.05 and 3.1, respectively.

^b The percentage in this column does not need to represent only the percentage of correct responses; it can represent any percentage, for example percentage of abstractions that were identified as off-label use or percentage of abstractions that had systemic lupus erythematosus (SLE).

the proportion of off-label use among users of MabThera during the entire study period in the 5 European countries of interest. The proportion of each of the most common off-label use indications will be described among the entire off-label use group. In addition, an estimate of off-label usage will be determined amongst prevalent (i.e., repeat infusions) and incident (i.e., patients attending for their first MabThera infusion) patients to the extent that incident use can be accurately determined. Characteristics of patients meeting the definitions for both strict and broad on-label use will also be evaluated. The dosage of MabThera used by infusion will also be estimated in the on- and off-label groups.

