8.9 LIMITATIONS OF THE RESEARCH METHOD

Selection bias is a distortion of evidence or data that arises from the method of collecting samples and data, in other words, resulting from the method by which study patients are selected. The selection bias may undermine the external validity (generalizability) of the study data and results. In this study, a selection bias may arise from:

- The method study sites are selected
- 2. The method patients at the individual sites are selected.

In order to minimize selection bias, the following site and patient selection methods are used. Ten (10) to 15 infusion centres in the participating European countries, preferably from diverse geographical regions within a country, that have prescribed MabThera to patients with non-oncology conditions during the (country-specific) eligibility period will be chosen (see also Section 8.2). A list of potential sites will be reviewed, and in situations where the number of identified sites is greater than the number required for the study, the selection of sites will be randomized. The process of site selection will be carefully documented.

Possible selection bias occurring at the patient level will be minimized by the following selection methods (see also Section 8.2):

- If a site had administered MabThera during the country-specific observation period to not more than 30 (eligible) patients, all these patients will be included in the study.
- If a site had prescribed MabThera during the (country-specific) observation period to more than 30 (eligible) patients, 30 (eligible) patients will be randomly selected from this site to avoid any potential clustering or period effect.

As is the case with all voluntary surveys, invited patients will self-select into the study, and volunteer bias may lead to an underestimate or overestimate of the level of patient awareness.

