RA1.	☐ Yes☐ No	•	A1, contin	nue with	RA1	a. If n	o, go to RA2. otrexate use:
		/	/		(dd/n	nm/yy	уу)
RA2.	ever take		ur necrosi	s factor	-alph	a inhi	treatment cycle, did the patient bitors (adalimumab, iximab)?
in time		r to the dat					ts for tests performed closest ion in the patient's current
RA3.	C-reactive	ve protein (CRP) leve	el at first	t Mab	Thera	infusion in the current
	treatmer	nt cycle:		mmol	/L		
	RA3a.	Date of CI	RP test:	/		/	(dd/mm/yyyy)
RA4.	Erythroc	yte sedime	ntation rat	te (ESR) at fi	rst Ma	abThera infusion in the current
	treatmer	nt cycle:	mm/h	r			
	RA4a.	Date of ES	SR:	/	/		(dd/mm/yyyy)

RA5.	Tender j	oint count (0 – 28) at first Mab	Thera infu	ısion in t	he current	treatment
	cycle:	joints				
	RA5a. (dd/mm/	Date of tender joint count:	/	/		
RA6.	Swollen	joint count (0 - 28) at first Mat	Thera inf	usion in	the curren	t treatment
	cycle:	joints				
	RA6a. (dd/mm/	,	/	/		
RA7.		e of extra-articular involvemen reatment cycle:	t at first M	labThera	a infusion i	n the
RA8.		ssessment of patient's genera) at first MabThera infusion in				scale (VAS)
		mm				
	RA8a. (dd/mm/	Date of global health assessr	ment:	/	/	

Medical Record Abstraction Form—Draft

For questions RA9 through RA14a, please provide results for tests performed on or nearest to the date of the patient's most recent MabThera infusion (Q6).

RA9. C-reactive protein (CRP) level at most recent MabThera infusion:

mmol/L Date of CRP test: RA9a. (dd/mm/yyyy) RA10. Erythrocyte sedimentation rate (ESR) at most recent MabThera infusion: mm/hr RA10a. Date of ESR: (dd/mm/yyyy) RA11. Tender joint count (0 - 28) at most recent MabThera infusion: joints RA11a. Date of tender joint count: (dd/mm/yyyy) RA12. Swollen joint count (0 - 28) at most recent MabThera infusion: joints RA12a. Date of swollen joint count: (dd/mm/yyyy) RA13. Presence of extra-articular involvement at most recent MabThera infusion: ☐ Yes □ No

	sessment of patient's general health or at most recent MabThera infusion:	n visu	al ar	nalogu	e scale	(VAS)
	mm					
RA14a. (dd/mm/y	Date of global health assessment:	/		/		

3. Patient Questionnaire - Draft

MabThera Risk Minimisation Programme Evaluation

Patient Questionnaire—Draft

Thank you for agreeing to participate in this study.

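### The drug utilisation cohort has two incompatible definitions: a 12-month look-back that includes patients who stopped, and an attendance rule that cannot admit them

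*Protocol*

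**What the plan says.** **Look-back cohort.** Section 8.1.1 sets a 12-month look-back before the index date, calls it the eligibility period, and reviews charts only up to that date. Figure 1 labels the cohort as all non-oncology patients treated before the index date. For consenting patients the observation period is "the interval between the first and last infusion dates of MabThera, if treatment is discontinued before the index date", so people who stopped are expected in the cohort. For smaller sites the rule in 8.9 reads "not more than 30 (eligible) patients, all these patients will be included in the study"; larger sites draw 30 at random.

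**Attendance cohort.** Section 8.2 lists one set of inclusion criteria for study entry. The first is "Patient is in the centre to receive an infusion for MabThera for a non-oncology indication during the study period". The Synopsis says "The study start date will be the date of the first data collection", meaning the first survey record or the start of chart extraction. Section 8.2 has coordinators find and consent patients around their infusion visits, and 9.2 requires signed consent before either component.

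**Incident use.** Section 8.6 plans an off-label estimate for "incident (i.e., patients attending for their first MabThera infusion) patients", as far as incident use can be determined. Later in the same section, in the exploratory analyses, incident means a first course.

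**Index date.** Section 8.1.1 makes it the start of abstraction for the first patient and also has it "correspond to the date when a site becomes aware of the study objectives".

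**Form.** For the later set of disease measures in RA patients, the draft abstraction form says "please provide results for tests performed on or nearest to the date of the patient's" most recent infusion. It gives no index-date limit.

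**The concern.** The main result of the chart component is the proportion of off-label use among MabThera users, produced in answer to a regulator's request. Its denominator depends on which of the two rules a site follows. One site could list everyone treated in the look-back and sample from that list. Another could enrol whoever comes for an infusion after data collection opens. These are different populations, and pooling them gives a proportion with no clear target.

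If both rules are applied, those lost are patients whose MabThera ended before the index date and patients who start after it. Off-label patients may be over- or under-represented among those who stopped. Section 8.9 discusses site selection, patient selection and volunteering, but not this restriction. A larger sample does not remove it.

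The two index-date definitions bear on a separate promise in 8.1.1, that the data are free of influence from study awareness. If the date used is the start of abstraction and the site knew the objectives earlier, part of the look-back falls after awareness.

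**Working it through.** **1. The rules side by side**

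| Patient | Look-back rule (8.1.1, Figure 1, 8.9) | Attendance rule (8.2, Synopsis) | Both |
|---|---|---|---|
| Infused in look-back, stopped before index date, no restart | in | out | out |
| Infused in look-back (including those who started in it), returns after index date | in | in | in |
| First infusion after index date | out: no MabThera data before the cut-off | in | out |

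Under both rules, the 8.1.1 provision for patients who discontinued before the index date applies to nobody except those who stopped and then restarted.

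**2. The plan's own precision figure**

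Inputs from 8.5: n = 1,500, 75% on-label (25% off-label). Table 1: 8 patients per centre, ICC 0 to 0.3.

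Half-width = 1.96 × √[p(1−p) × DE / n], with DE = 1 + (m−1) × ICC.

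- ICC 0: 1.96 × √(0.1875/1500) = 2.2 points, giving 72.8% to 77.2% as stated.
- ICC 0.3, m = 8: DE = 3.1; 1.96 × √(0.1875 × 3.1/1500) = 3.9 points, as in Table 1.
- The chart component plans 20-30 patients per centre. With m = 30 and ICC 0.3, DE = 9.7 and the half-width is 6.8 points.

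**3. Possible bias (assumed inputs)**

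The protocol gives neither the share s of look-back users who do not return nor their off-label rate x. Take 25% off-label among returners, matching the protocol's 75% on-label example.

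All-user proportion = (1−s) × 25% + s × x, so it differs from the returners' figure by s × (x − 25%).

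| s | x = 15% | x = 25% | x = 35% | x = 50% |
|---|---|---|---|---|
| 10% | 24.0 | 25.0 | 26.0 | 27.5 |
| 20% | 23.0 | 25.0 | 27.0 | 30.0 |
| 30% | 22.0 | 25.0 | 28.0 | 32.5 |
| 40% | 21.0 | 25.0 | 29.0 | 35.0 |

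The returners' 25% is thus between 4 points too high and 10 points too low. To exceed 2.2 points, the off-label rates must differ by 2.2/0.2 = 11 points when 20% do not return, or 2.2/0.4 = 5.5 points when 40% do not. To exceed 3.9 points, the gaps are 19.5 and 9.75 points.

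**4. Index date**

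Abstraction follows ethics approval (8.1.1, 9.3). Before that, centres are contacted, their interest is assessed and their card-distribution practice is recorded (8.2), and centre staff may themselves submit the protocol to the ethics committee (9.3). Figure 1 lists site selection and contracting under start-up. A site will therefore ordinarily know the objectives before it abstracts its first record.

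**The case against.** The strongest reply is that the target is not clearly the look-back cohort. Study period is never formally defined. Section 8.6 states the main analysis for users during the entire study period, the phrase that criterion 1 also uses, and one paragraph of 8.1.1 ties abstraction to a 10-month data collection period. On that reading, attendance is the intended definition. In 8.9, the bracketed word eligible can also be read as already filtered by 8.2. This stands to the extent that the documents do not settle which cohort is meant. It does not remove the conflict, because the look-back, the chart cut-off and the provision for discontinued patients then have no proper role. Section 8.2 also mentions recruitment at a scheduled visit. That could reach someone who has stopped, but that person would still fail criterion 1.

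Several stronger readings are tempting and are not supported:

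- *No incident users can be evaluated.* Patients who started within the look-back and returned are abstracted, and item 5 of the form (date of first infusion) identifies them. Only those first infused after the index date are lost.
- *Off-label use will be understated by a given amount.* The inputs are not in the documents and the sign can reverse.
- *Form items without a cut-off distort the off-label proportion.* Section 8.3 classifies use by disease. The form is a draft open to revision after piloting, and 8.1.1 already states the cut-off. The gap matters for dose, infusion counts and disease activity.
- *Patients from MabThera trials should be removed from the chart component.* Section 8.2 says "No Exclusion criteria will apply for medical record abstraction participation". That is a stated choice, not a contradiction.
- *The two index dates can never coincide, or differ by a known interval.* This is inference. The protocol fixes no date on which a site learns the objectives.

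**Conclusion.** The contradiction is present in the current text and needs resolving before sites build their lists. Sections 8.1.1 and 8.9 count patients whom 8.2 cannot admit. The conclusion that only returning users remain holds when 8.1.1 and 8.2 are applied together; which cohort sites would actually assemble is unresolved.

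The documents determine neither the size nor the direction of the bias. It is nil if non-returners have the same off-label rate as returners. It passes the stated 2.2-point half-width under moderate assumptions, but need not pass the wider interval that clustering implies. The case for change rests on the undefined denominator, not on any particular number of points.

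The double index date is a lesser but real fault: as written, freedom from awareness effects is asserted and not secured.

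**What to change.** 1. **Eligibility.** Give the chart component its own criterion: at least one non-oncology MabThera infusion in the 12 months before the site's index date. Keep attendance as a criterion for the survey only. Allow consent to abstraction at any visit or by another route the ethics committee approves. If non-attenders cannot be consented, restate the target in 8.6 as look-back users who return after the index date, list the restriction in 8.9, and report the aggregate number of look-back users not reached where local rules permit. Do not log indication for patients who were never asked: 8.2 and 9.2 require consent, and the logs cover only patients approached.
2. **Incident use.** Define it for the chart component as a first-ever infusion (form item 5) within the look-back, and reconcile the two definitions in 8.6.
3. **Index date.** Use one definition, no later than the day the site is told the objectives of this protocol version. Do not tie it to the feasibility contact: those results are already in version 1.0 of July 2012, so the look-back could precede the March 2013 GPA/MPA approval. Carry the 8.1.1 cut-off into the form's most-recent items (2, 6, 11 and RA9-RA14), and anchor the past-period items (10 and 12) to the same date.

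The cost is wording in the protocol and form, plus an ethics submission for any consent route outside visits. An earlier index date lengthens the gap before consent, so somewhat more look-back users may be out of reach. The fallback costs only a narrower stated population and one reported count.

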8.3 VARIABLES

Medical Record Data

The site will abstract information from the medical record for each of the DUS consenting patients and will enter the abstracted information in an electronic case report form (eCRF):

- Study ID (identification), age, sex
- Condition for which MabThera has been prescribed (via checklist):

- RA
- Ankylosing spondylitis
- Psoriatic arthritis
- Undifferentiated spondyloarthritis
- Juvenile idiopathic arthritis
- SLE
- Systemic vasculitis
- Inflammatory myopathies
- Behçet disease
- Sjögren syndrome
- Nephrotic syndrome
- Reason for MabThera prescription:
 - Failure of previous treatment
 - Adverse events (AEs) under previous treatment
 - Compassionate use
- Date of first diagnosis of the condition
- For patients with RA, severity of RA as measured with the DAS28 (28-joint Disease Activity Score). To calculate the DAS28, the following items will have to be abstracted from the medical record:
 - C-reactive protein level
 - Erythrocyte sedimentation rate
 - Number of tender joints
 - Number of swollen joints
 - Global assessment of patient's general health on the visual analogue scale (VAS) (0–100)
 - Presence of extra-articular involvement
- MabThera dosage for the most recent infusion and number of MabThera infusions in the past 2 years
- Other current and previous anti-inflammatory medication including biological agents other than MabThera
 - Methotrexate (key variable for on- or off-label classification of MabThera use)

- Glomerulonephritis
- Multiple sclerosis/neuromyelitis optica
- Pemphigus vulgaris
- Polydermatomyositis
- Mixed connective tissue disease
- Wegener's GPA/ MPA
- Eosinophilic GPA
- Other (specify)

- Immunosuppressives: prednisolone, glucocorticoid bolus therapy, methylprednisolone, methotrexate, cyclophosphamide, azathioprine, mycophenolate mofetil, intravenous immunoglobulin, plasmapheresis, other immunosuppressives (specify)
- Non-steroidal anti-inflammatory drugs (NSAIDs), including cyclooxigenase (COX)-2 inhibitors
- Biological agents:
 - TNF-alpha inhibitors (key variable for on- or off-label classification of MabThera use): etanercept, infliximab, adalimumab, golimumab, certolizumab pegol, ocrelizumab
 - Interleukin inhibitors: tocilizumab, anakinra
 - Abatacept
 - Janus kinase (JAK) inhibitor: tofacitinib
 - Other biological agents (specify)

A "data not available" response will be available where appropriate for those record abstraction items for which data may be missing from patient records. This type of response will help reduce missing data and will document the overall gaps in record keeping.

A brief pilot test of the translated version of the abstraction form will be conducted in each country, and the abstraction form in one or more countries may be adjusted based on the results of this pilot.

A draft version of the medical record abstraction form is included with this document (Appendix 1).

Off-Label Use Definition

The definition of off-label use of MabThera will be based on the use for a non-oncology disease or medical condition other than RA and GPA/MPA covered by MabThera SPC.

In absence of labelled indications, potential off-label use could include, but is not limited to, the following conditions:

- Ankylosing spondylitis
- Psoriatic arthritis
- Undifferentiated spondyloarthritis
- Juvenile idiopathic arthritis
- SLE
- Systemic vasculitis

- Eosinophilic GPA
- Inflammatory myopathies
- Behçet disease
- Sjögren syndrome
- Nephrotic syndrome
- Glomerulonephritis
- Multiple sclerosis/neuromyelitis optica
- · Pemphigus vulgaris
- Polydermatomyositis
- · Mixed connective tissue disease

Patient Survey data

The patient questionnaire has been developed following standard survey methodological principles and will be cognitively tested with patients in each of the target countries. Modifications will be made to the questionnaire based on the results of testing, and some variations to the questionnaire are anticipated based on country-specific requirements.

The questionnaire will include an introductory section with questions to confirm eligibility. The majority of the questionnaire items will be closed ended, ensuring that the resulting data are easy to analyse and interpret. Closed-ended questions are generally more efficient than open-ended questions (or open-ended text fields) and more conducive to summarisation and statistical analyses.

The questionnaire will collect the following information (please refer to Appendix 1 for the draft questionnaire):

- Demographics (e.g., age, sex, ethnicity)
- Patient previous history of PML or other serious infectious diseases
- Whether the patient has received a previous treatment with MabThera, if so, number of prior infusions during the last 12 months
- Patient understanding or awareness of the following:
 - Known and potential risks of infection associated with MabThera including the risk of PML
 - -Symptoms of infection, including PML, and what actions patients should take
 - -Who should not be treated with MabThera
 - -What medication information patients should tell their doctor
 - -Any other counselling received for the infections covered in the PAC
- Patient receipt and reading of the PAC

- -How often has the patient received the PAC?
- –Does the patient currently have a PAC?
- Has the patient received a package leaflet (i.e., PIL)? Does the patient currently have one?
- Patient receipt of additional safety-related information about MabThera
- Patient actions and any changes in behaviour triggered by the PAC (for example, if the patient consulted another physician following the first MabThera treatment or if the patient showed the card to a doctor other than one associated with the MabThera treatment).

Other descriptive information about the patient will be collected to enable stratification of results and facilitate comparison of study participants with the total sample of patients receiving MabThera at participating sites.

Patient Questionnaire Administration

The questionnaire will be completed after the patient arrives at the centre and before the start of the infusion to make sure the questionnaire is completed before any additional counselling regarding the content of the PAC is provided by the site. According to the responses to the feasibility evaluation, all sites considered this to be feasible considering their infusion and counselling practices.

The patient questionnaire will be self-administered (closed-ended questions with predefined answers) on a hard-copy form at the site. The questionnaire will be translated into each local language (English, French, German, Italian, and Spanish) and pretested. Although there are a number of advantages to using an electronic format for questionnaire administration, based on the results of the feasibility evaluation, paper data collection forms are the most efficient approach for this study given the centres' preferences, infrastructure, and the number of patients per centre. Written informed consent will be obtained from each patient prior to completion of this questionnaire.

Patients will be asked to complete the questionnaire in a private setting within the infusion centre. Sites will provide patients with appropriate privacy so there is no influence by the physician (or patient perception thereof) in this process. Patients will place their completed questionnaires in an envelope and give the sealed envelope to a study coordinator or designee. Although participating physicians will be informed of the purpose of the study, they will be counselled not to alter routine practice and patient education so as not to influence the study results. Physicians will be advised that the ultimate goal of the study is to evaluate the use of the PAC.

Pretesting of the Patient Questionnaire

To evaluate the patient questionnaires before fielding the study, cognitive pretesting with physicians and patients will be conducted in each country and in each local language. Cognitive pre-test interviewing is a well-established qualitative research methodology

used to identify problems with survey questions and response options (Groves, 2009). Specifically, trained interviewers will ask pre-test participants to complete the questionnaire while thinking aloud or describing their thought processes as they answer the questionnaire items. Pre-test interviewers will use an interview guide that includes probe questions designed to help interviewers understand how each participant interpreted and chose his or her answers for each item in the draft questionnaires. The pre-test interviews will be designed to help identify problems with survey questions, wording, response choices, etc., and ensure that respondents understand the questions. The pre-test interview data will be used to optimise the language used in the questionnaire prior to implementing the patient surveys.

